### 4.3 Concomitant Medication

No concomitant medications will be recorded, with the exception of rescue medications, as noted below.

#### **4.4 Rescue Medication Administration**

All the rapid response equipment and resuscitation staff are readily available 24/7 in the intensive care unit setting at Children's Hospital of Philadelphia. In the rare event that a significant allergic reaction occurs, or anaphylaxis results following injection of Lumason™, standard clinical medication to treat the subject will be administered. For presumed allergic reactions, medications may include intravenous diphenhydramine and bolus corticosteroids (prednisolone), based on clinical care. For anaphylaxis, medications may include epinephrine as well as fluid and oxygen administration for emergency treatment, based on clinical care decision making and on the severity of symptoms. Any severe allergic or anaphylactic reaction will be reported to both the IRB and the FDA.

#### **4.5 Subject Completion/Withdrawal**

Subjects' families may withdraw their child from the study at any time without prejudice to their child's care. A study investigator may withdraw a subject to protect the subject for reasons of safety or for administrative reasons. It will be documented whether or not each subject completes the clinical study. If the investigator becomes aware of any serious, related adverse events after the subject completes or withdraws from the study, the adverse events will be recorded and reported.

##### **4.5.1 Early Termination Study Visit**

A subject may be withdrawn by a parent prior to or during a CEUS scan, provided the 60 minute monitoring is completed after injection of the investigational drug. The CEUS examination will be terminated if there is a deterioration in the subject's clinical status during imaging.

##### **4.5.2 Review of medical records from EPIC and/or other sources**

- Date of birth
- Weight
- Clinical diagnosis
- Treatment history (medications, chemotherapy, antibiotics, steroids)
- Surgical history
- Pathology report

##### **4.5.3 Review of diagnostic images from the PACS (iSite Radiology or iSite Enterprise)**

- Review of abdominal ultrasound and CEUS images (iSite)

### **5 STUDY EVALUATIONS AND MEASUREMENTS**

The results of the pre-contrast injection and CEUS imaging will be collected for research purposes only. The results of the CEUS will not be used to direct clinical care decisions,

without confirmation of diagnosis by another medically established diagnostic product or procedure.

#### Qualitative analysis

Visual rating by 2 teams consisting of primary investigator and second radiologist (co-investigator). Each scan will be rated for diagnostic quality and qualitative rating of bowel perfusion. The visual rating scale used will be: 0 (absent flow), 1 (decreased flow), 2 (normal flow), 3 (increased flow).

#### Quantitative analysis

Qontrast (Bracco Diag Inc., 510K regulatory status granted in 2004) contrast quantification software or similar software will be used to analyze the obtained CEUS scans. For each scan, wash-in and wash-out curves will be generated to quantify the rate of wash-in, time to peak intensity, peak intensity, and area under the curve.

The CEUS scans will be interpreted by the sponsor-investigator, and a second interpretation by a “second reader” in Radiology, who is part of a group of radiologists with sufficient training and expertise to read CEUS scans.

#### Monitoring After Investigational Drug Administration:

The monitoring post-administration will encompass 60 minutes, during which time the subject will be observed for the occurrence of infusion reactions. Any concern by the investigative team or attending staff for severe allergic reaction or anaphylaxis will be managed as all similar reactions are managed as part of clinical care, with close observation and treatment as clinically indicated, which may include diphenhydramine, corticosteroids, fluids, oxygen and epinephrine. Post-infusion reactions will be recorded and reported following established IRB and FDA reporting guidelines.

## **6 STATISTICAL CONSIDERATIONS**

Up to 100 evaluable patients should be adequate for assessment of clinical feasibility and optimization of protocol. Qualitative analysis will be used as detailed above.

Quantitative analysis will be performed by drawing a region of interest in bowel segments and compared to control subjects (those with suspected or at risk of necrotizing enterocolitis but turns out to be normal on imaging and clinical evaluation) using non-parametric Wilcoxon testing.

### **6.1 Primary Endpoint**

The primary objective of this study is to evaluate whether CEUS technique can be utilized to detect early alterations in bowel perfusion in NEC. The differences in bowel perfusion between normal subjects (those with suspected or at risk of necrotizing enterocolitis but turn out to be normal on imaging and clinical evaluation) versus NEC patients will be assessed qualitatively and quantitatively using the CEUS technique, as detailed above.

## 6.2 Secondary Endpoints

Diagnostic quality of the CEUS exams will be evaluated with the scoring system of non-diagnostic (1), moderate artifacts degrading diagnostic quality (2), mild artifacts without degradation of diagnostic quality (3), and diagnostic (4). As a gold standard for NEC diagnosis, surgical findings (in those subjects undergoing surgery as part of clinical care) or Bell's staging criteria for NEC in combination with radiographic and clinical signs (for subjects not undergoing surgery) will be used.

## 6.3 Statistical Methods

### 6.3.1 Baseline Data

Baseline and demographic characteristics will be summarized by standard descriptive summaries.

### 6.3.2 Safety Analysis

All subjects entered into the study, who receive at least one dose of investigational drug per CEUS scan will be included in the safety analysis. The frequencies of AEs by type, severity, and temporal relationship to the CEUS scan will be summarized. SAEs (if any) will be described in detail.

Adverse events will be recorded at 1) 60 minutes post-scanning when the monitoring period is completed, and 2) through 48 hours post-scanning, with documentation at 48 hours post-scanning if no adverse event presents until this point.

## 6.4 Sample Size and Power

As noted in the main text, no previous study has used contrast ultrasound to examine bowel wall perfusion. For power analyses, estimates of group differences were obtained from a study that provided mean perfusion values for a control group using Doppler ultrasound. Although contrast ultrasound and Doppler ultrasound rely on different methods to quantify perfusion (contrast quantifies by absolute intensity and Doppler quantifies by counting the color signal) the methods are similar enough that Doppler findings can inform the present study (and of note, given that contrast ultrasound is more sensitive, power analysis based on the Doppler findings are considered to be conservative). Given the reported bowel perfusion mean and standard deviation value for controls of 3.78 (SD = 1.1) [1], assuming a moderate effect (Cohen's D = 0.71), a sample size of 40 per group would provide power = 0.88 (alpha = 0.05). Since each subject has a clinical care US (control group) followed by a research CEUS (experimental group), each subject will serve as its own control. Since the CEUS method has not been applied to NEC imaging before, an interim statistical analysis may be considered to review image quality and comparisons between the results of each subject's CEUS scans and any available clinical US exams, to better inform the number of subjects required for statistical significance.

## 7 STUDY DRUG

### 7.1 Description

Lumason™ is currently FDA approved for use in the pediatric population for echocardiography and evaluation of focal hepatic lesions, and very recently (Jan 2017) approved for use in children for the evaluation of the urinary tract in pediatric patients with known or suspected vesicoureteral reflux. Previously, the presence of cardiac shunts was a contraindication for its use, but this was recently cancelled by the FDA as of December 2016. However, for this clinical study, the FDA has recommended that subjects with hemodynamically significant PDA and right-to-left cardiac shunts be excluded from study participation. Ultrasound contrast agents have been approved for use in Europe for almost two decades. In the case of SonoVue (now called Lumason™), a second-generation lipid/sulfur hexafluoride US contrast agent (Bracco, Milan, Italy), the European Union approved its intravenous use in adults in 2001. The FDA in the United States just recently approved the use of Lumason™ for evaluation of focal hepatic lesions in the pediatric population in 2016. Through decades of clinical utilization of ultrasound contrast agents, there are established recommended doses for the intravenous route of administration. Recommended intravenous dose for Lumason™ is weight-based, 0.03mL/kg as an intravenous injection. As an example, for the intended study population it may be roughly estimated that the maximum weight of an infant 1 year of age may be up to approximately 10 kg, for a maximum dose of 0.30 mL. Two injections per exam will be performed.

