Glycerol), Sodium Salt (0.19 mg in 1 mg). Inactive ingredients include Polyethylene Glycol 4000 (strength 24.56 mg in 1 mg) and Palmitic Acid (0.04 mg in 1 mg). The Sulfur hexafluoride lipid microspheres are composed of SF6 (molecular weight 145.9) gas in the core surrounded by an outer shell monolayer of phospholipids consisting of 1,2-Distearoyl-sn-glycero-3-phosphocholine (DSPC) and 1,2-Dipalmitoyl-sn-glycero-3-phosphoglycerol, sodium salt (DPPG-Na) with palmitic acid as stabilizer. Sulfur hexafluoride lipid-type A microspheres fall under Category B, that is, animal reproduction studies have failed to demonstrate a risk to the fetus and there are no adequate and well-controlled studies in pregnant women. 1,2-Distearoyl-sn-glycero-3-phosphocholine (DSPC), with empirical formula C44H88NO8P, has a molecular weight of 790.6. 1,2-Dipalmitoyl-sn-glycero-3-phospho-rac-glycerol sodium (DPPG-Na), with empirical formula C38H74 NaO10P, has a molecular weight of 745.

---

Study Design	Single site, open-label clinical study.
Subject Population	Inclusion Criteria
key criteria for Inclusion and Exclusion:	
 
1. Males and females aged 1.5 years or younger
 
2. Post menstrual age of 29 weeks or older
 
3. Patients with suspected or diagnosed necrotizing enterocolitis
 
4. Patient in the CHOP NICU or PICU
 
5. Parental permission
 

	Exclusion Criteria
	
 
1. Medical history of Lumason hypersensitivity
 
2. Hemodynamic instability as defined by rapid escalation of cardiopulmonary support in the past 12-24 hours, as defined by the clinical care team including <math>\geq 1</math> intensive care physician not part of the study team
 

---

---

3. Pulmonary insufficiency as defined by FiO2 requirements of >40% and/or subjects with pulmonary hypertension requiring nitric oxide

---

**Number Of Subjects** 200; CHOP will be the only site of the study.

---

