### **3.5.2 Exclusion Criteria**

1. Medical history of Lumason hypersensitivity
2. Hemodynamic instability as defined by rapid escalation of cardiopulmonary support in the past 12-24 hours, as defined by the clinical care team including  $\geq 1$  intensive care physician not part of the study team
3. Pulmonary insufficiency as defined by FiO2 requirements of  $>40\%$  and/or subjects with pulmonary hypertension requiring nitric oxide

In this regard, there is a published report of infusion of the investigational drug in twelve neonates, ranging from 26.9 to 41 weeks gestational age, including four premature infants from 26.9 to 29.5 weeks gestational age [9] as well as 3 additional premature subjects from unpublished data of the sponsor. The infusion of the investigational drug in these neonates and premature infants was safe, and imaging results of good quality.

Subjects who do not meet all of the enrollment criteria may not be enrolled. Subjects will be excluded from the study, if in the judgement of the primary clinical team, they are too unstable to tolerate the procedure.

Any violations of these criteria must be reported in accordance with IRB Policies and Procedures.

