### **Steps Taken to Minimize Risks**

Parents and/or legal guardians of participants will be asked about contraindications to contrast enhanced ultrasonography examinations, as listed in the exclusion criteria. In order to appropriately treat potential rare adverse events, patients will be monitored by the study team for 60 minutes following contrast administration.

Vital signs will be recorded from the medical chart and in-place monitoring and documented at 1) 30 minutes post-scanning, and 2) 60 minutes post-scanning. During monitoring, subjects will be assessed for rash, allergic reactions, anaphylaxis, and abrupt deviations from the subject's baseline hemodynamic parameters trend not related to medical intervention.

Adverse events will be recorded at 1) 60 minutes post-scanning when the monitoring period is completed, and 2) through 48 hours post-scanning, with documentation at 48 hours post-scanning if no adverse event presents until this point.

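### The FDA's recommended exclusion of significant PDA and right-to-left shunts appears in Section 7.1 but not in the exclusion criteria used to screen infants

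*Combined protocol and SAP*

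**What the plan says.** Section 7.1 (Description) notes that cardiac shunts used to be a contraindication to the contrast agent and that the FDA lifted this in December 2016. It then makes an exception for this trial: "the FDA has recommended that subjects with hemodynamically significant PDA and right-to-left cardiac shunts be excluded from study participation".

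Section 3.5.2 lists three exclusions, and the Protocol Synopsis repeats them:

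1. "Medical history of Lumason hypersensitivity"
2. "Hemodynamic instability as defined by rapid escalation of cardiopulmonary support in the past 12-24 hours", as judged by the clinical care team, including at least one intensive care physician outside the study team
3. "Pulmonary insufficiency as defined by FiO2 requirements of >40% and/or subjects with pulmonary hypertension requiring nitric oxide"

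Below the list, Section 3.5.2 adds a discretionary exclusion: "Subjects will be excluded from the study, if in the judgement of the primary clinical team, they are too unstable to tolerate the procedure". It also says "Subjects who do not meet all of the enrollment criteria may not be enrolled", and it requires violations of the criteria to be reported under IRB policy.

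Section 4.1 has the study team review medical records against the inclusion and exclusion criteria and discuss each case with neonatologists. Under the steps to minimize risk in Section 9.4.1, parents "will be asked about contraindications to contrast enhanced ultrasonography examinations, as listed in the exclusion criteria".

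**The concern.** The recommendation is specific to this study and was made despite the relaxed label, so it cannot be read as leftover label language. Yet it sits only in a paragraph describing the drug, which no screening step refers to. The lists that decide who is enrolled do not mention PDA or shunts.

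Section 9.4.1 rates giving the drug as a minor increase above minimal risk with no prospect of direct benefit. It also notes that serious cardiopulmonary reactions, some fatal, have occurred in adults with complex comorbidities, and that unstable cardiopulmonary conditions may raise the risk. Section 4.2 makes worsening cardiopulmonary status and worsening pulmonary hypertension adverse events of special interest. Under Section 8.8 any serious adverse event, related or not, temporarily stops the study for discussion with the FDA. Such an event in an infant whom the FDA had advised leaving out would be hard to defend.

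There is also a monitoring consequence. The reporting duty in Section 3.5.2 attaches to the criteria listed there. Enrolling an infant with a shunt breaks none of them, so it would probably not be recorded as an eligibility violation.

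**Working it through.** The plan gives no figure to reproduce, and the point depends on no power or sample size calculation. The check is a comparison of text, followed by a bound on exposure.

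**Step 1. Do the listed criteria cover the condition?**

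| Route to exclusion | What triggers it | Names PDA or shunt? |
|---|---|---|
| Criterion 1 | Past hypersensitivity to the agent | No |
| Criterion 2 | Rapid escalation of support within 12-24 hours | No |
| Criterion 3 | FiO2 above 40%, or pulmonary hypertension on nitric oxide | No |
| Clinical team's discretion (3.5.2) | Too unstable for the procedure | No |

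The result is 0 of 3 listed criteria in Section 3.5.2 and 0 of 3 in the synopsis.

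**Step 2. Does another step before injection catch it?**

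- Section 4.1: record review is against the listed criteria.
- Sections 3.1.1 and 9.5: eligibility is confirmed by chart review, and no cardiac check is named.
- Section 9.4.1: the questions to parents refer back to the same list.
- Section 4.5.2: the record items include clinical diagnosis but no echocardiogram or cardiac finding by name.
- Section 4.2: echocardiography appears only among possible signs of worsening pulmonary hypertension in the 48 hours after scanning.

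No step before injection asks about a shunt.

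**Step 3. Test a case.** Take an infant in the NICU with suspected NEC and a hemodynamically significant PDA or right-to-left shunt, on unchanged support for more than 24 hours, with FiO2 of 40% or less, no nitric oxide and no hypersensitivity. Criteria 1, 2 and 3 are not met. The discretionary exclusion turns on instability, and this infant is stable. If the inclusion criteria are met and the parents consent, the infant is eligible.

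**Step 4. Bound the exposure.**

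- Per infant: 2 exams × 2 injections = 4 injections at most. The second exam is optional.
- Whole study: 200 infants × 4 = 800 injections at most. This is a ceiling for all subjects, not for those with shunts.
- Number affected: the documents give no prevalence. If 5% to 20% of the 200 enrolled infants had such a shunt, the count would be 0.05 × 200 = 10 to 0.20 × 200 = 40. The 5-20% range is an assumption for illustration. If it described infants screened rather than enrolled, fewer would be affected, because the existing criteria would remove some of them.

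**The case against.** The mismatch in the text is not in dispute. The case on the other side concerns its force.

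- **It is a recommendation, not a requirement.** Section 8.8 uses the language of requirement for the FDA's stopping rule, while Section 7.1 speaks only of a recommendation. The FDA correspondence is not available, so the recommendation may have been superseded or met through the cardiopulmonary criteria. That uncertainty is real. But the current text presents the recommendation as standing, and nothing in the protocol declines, replaces or explains it.
- **Existing safeguards overlap with it.** Criteria 2 and 3, the clinical team's discretion and the case discussion with neonatologists would remove some infants with significant shunts. This stands in part. Each listed route turns on instability, oxygen need or nitric oxide, so the stable infant in the test case remains.
- **Safety monitoring is close.** There is 48-hour follow-up for events of special interest, a safety analysis after 10 subjects (Section 8.1) and a stop after any serious adverse event. All of these act after an injection and do not replace an eligibility criterion.
- **Section 7.1 is part of the protocol.** Section 1.3 commits the investigators to follow the protocol and to document noncompliance, so enrolling such an infant might be recorded that way. This is arguable, but Section 7.1 reports advice from the FDA and gives the study team no instruction.
- **The numbers are soft.** This stands. The 10-40 range has no basis in the documents, and 800 is a ceiling for the whole study. The finding rests on neither.

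**Conclusion.** The concern holds and should be resolved before further enrolment. A study-specific FDA safety recommendation is stated in Section 7.1 and missing from both exclusion lists and from every screening step. As written, a stable infant with a significant PDA or right-to-left shunt, on FiO2 of 40% or less and without nitric oxide, can be enrolled and injected.

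The firm measure of size is 0 of 3 listed criteria. How many infants this affects is unknown. The conclusion assumes that Section 7.1 states the FDA's current position, which cannot be confirmed from the documents. If that position has changed, the defect is an outdated statement in Section 7.1, and it still needs correcting. Sample size and power assumptions are not affected.

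**What to change.** Reconcile Section 7.1 with Section 3.5.2, the synopsis and Section 4.1 in one of two ways:

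1. **Adopt the recommendation.** Add hemodynamically significant PDA and right-to-left cardiac shunt as a fourth exclusion in Section 3.5.2 and the synopsis. Add a matching line to the eligibility check in Section 4.1, assessed from the cardiac findings in the records already reviewed at screening, and say what is done when the chart is silent. The parent check in Section 9.4.1 and the violation reporting in Section 3.5.2 then apply without further edits, since both refer to the list.
2. **Withdraw the statement.** If the FDA no longer recommends this for the study, say so in Section 7.1 and give the basis.

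The first option is the safe default unless the FDA's changed position can be documented. It costs one criterion line in two places, one checklist item and a small loss from the eligible pool.

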### 7.2 Dosing

Through decades of clinical utilization of ultrasound contrast agents, there are established recommended doses for the intravenous route of administration. Recommended intravenous dose for Lumason™ is weight-based, 0.03mL/kg as an intravenous injection, up to a maximum of 2.4mL per injection. As an example, for the intended study population it may be roughly estimated that the maximum weight of an infant 1 year of age may be up to approximately 10 kg, for a maximum dose of 0.30 mL. Two injections per exam will be performed. Since investigational findings are subject to pre-analytic variability, performing two contrast-agent injections facilitates validation of findings if reproducibility is found. No increased risk was found at initial experience at Johns Hopkins Hospital, where 5 of 10 patients required double injection of contrast-agent. Clinical cases at Johns Hopkins Hospital and The Children's Hospital of Philadelphia have required double injection due to variable factors such as microbubble trapping within intravenous tubing. Adverse effects are not dose-dependent, thus risk is not increased by modifying the timing of interventions or increasing the number of contrast-agent injections.

Even though the initial dosing of investigational drug for this study is 0.03 mL/kg, it is possible that the optimal dose for CEUS imaging of hypoxic ischemic injury may be less than 0.03 mL/kg. Since there would be no apparent safety concern regarding the administration of a lower dose of the investigational drug, the study team would proceed with a lower dose administration, if initial imaging studies suggest that a dose less than

0.03 mL/kg may provide more optimal imaging results. Therefore, the study team proposes that a dose range of 0.01-0.03 mL/kg be considered for dose optimization of the initial subjects, as indicated. Based on the published report of safe infusion of the investigational drug in four premature infants from 26.9 to 29.5 weeks gestational age [15] as well as 3 additional premature subjects from unpublished data of the sponsor, this dose range seems appropriate. For each subject, the dose per injection, as well as the total dose delivered, will be recorded in the study file for each administration of study drug. The expectation is that the intravenous injection of this ultrasound contrast agent will permit noninvasive, non-ionizing delineation of physiology and pathophysiology with higher resolution and accuracy than conventional ultrasound techniques. Since preliminary studies at Hopkins showed that half of neonates required two injections of contrast agent to achieve evaluable CEUS images, two injections will be performed per CEUS scan in all subjects to ensure adequate image quality and reproducibility.

